### **8.1.14. Pharmacokinetic Assessment**

Blood samples for analysis of leuprolide concentrations as well as basal LH, FSH, testosterone and estradiol concentrations will be processed by a central bioanalytical laboratory. Date and time of each sample will be recorded.

## **8.2. Efficacy Endpoints and Assessments**

### **8.2.1. Primary Efficacy Endpoints and Assessments**

As described in the Study Methods section, subjects will at minimum undergo Part A of the study where two treatment injections separated by six months will be given starting at Visit 1 (Day 0); an Abbreviated GnRHa Stimulation Test six months after a subject's first treatment injection will be used to determine treatment efficacy; and a 12 month follow-up will occur. Alternatively subjects will undergo the first six visits of Part A and then at Visit 7 (Month 11) undergo Part B of the study (if invoked). In Part B of the study an additional two treatment injections separated by 5 months will be given starting at Visit 7 (Month 11), and an GnRHa Stimulation Test five months after the fourth treatment injection (i.e., at the 21st month visit) will be used to determine treatment efficacy at the end of the study. Two primary endpoints are defined contingent upon the invocation of Part B.

- If only Part A is carried out, the primary endpoint is defined as the percentage of subjects with serum LH concentrations < 4 mIU/mL at 30 minutes following an abbreviated GnRHa Stimulation Test at Visit 5 (Month 6). LH concentrations < 4 mIU/mL are considered prepubertal. The Investigational Product, Leuprolide Acetate 45 mg, will be considered effective for the treatment of children with CPP if ≥ 80% of subjects exhibit LH suppression < 4 mIU/mL at the Month 6 visit.
- If Part B is invoked, the primary endpoint is defined as the percentage of subjects with serum LH concentrations < 4 mIU/mL at 30 minutes following an abbreviated GnRHa Stimulation Test at Visit 11 (Month 21). Leuprolide acetate 45 mg will be considered effective for the treatment of children with CPP if ≥ 80% of subjects exhibit LH suppression < 4 mIU/mL at the Month 21 visit.

### **8.2.2. Secondary Efficacy Endpoints and Assessments**

Serving as secondary endpoints will be the following variables.

- The percentage of subjects with serum LH concentrations < 4 mIU/mL at 30 minutes following an abbreviated GnRHa Stimulation Test for any available measurement other than the measurement constituting the primary outcome variable (see above).
- The percent change from baseline in height at each available post-baseline measurement. Percent change is defined as  $((\text{change from Baseline})/(\text{Baseline})) \times 100$ .
- The growth velocity of height in cm/year at each available post-baseline measurement. Growth velocity is defined for each visit as  $(\text{change from Baseline})/[(\text{number of weeks since Baseline})/52]$ .
- The ratio of bone age at each given measurement point to chronological age at the same measurement points.
- Baseline to end-of-study stage shifts for each Tanner category.
- The percent change from baseline in hormonal concentration (LH, FSH, Testosterone, and Estradiol) at each available post-baseline measurement. Percent change is defined as  $((\text{change from baseline})/(\text{baseline})) \times 100$ .
- The percent change from baseline in systemic leuprolide concentration at each available post-baseline measurement. Percent change is defined as  $((\text{change from baseline})/(\text{baseline})) \times 100$ .

### **8.3. Pharmacokinetic/Pharmacodynamic Endpoints and Assessments**

The primary pharmacokinetic (PK) endpoint is Leuprolide concentration. Secondary PD endpoints are the changes in LH, FSH, testosterone and estradiol concentrations due to the leuprolide acetate injections. At Visit 1 concentration at multiple time points will be collected at  $\geq 30$  minutes prior to treatment injection, and at 1 hours ( $\pm 5$  minutes), 4 hours ( $\pm 10$  minutes) and at 6 hours ( $\pm 15$  minutes) after treatment injection. Basal concentration at a single time point per visit will be collected within a 28 day screening period and at all visits subsequent to Visit 1.

#### **8.3.1. PK/PD Parameters**

The following *PK/PD parameters will serve as endpoints.*

- *Visit 1 (baseline, 1 hr, 4 hrs, 6 hrs)*
  - Concentration Value at each time point
  - AUC over six hours
  - Cmax over six hours
  - Tmax over six hours
- *Basal Measurement over Study Period (Screening, first Visit 1 measurement, Visit 2 and greater)*
  - Concentration Value at each visit
  - AUC (over study period (i.e., 0 to infinity))
  - AUC (over set time periods (e.g. 0 to 6 hours, 0 to 6 mo, Day 7 to 6 mo))
  - Cmax (post each treatment administration)
  - Tmax (post each treatment administration)
- *Post GnRHa stimulation (screening; Visits 3, 5, 6 and 8 in Part A; Visits 7, 9 and 11 in Part B))*
  - Concentration Value of LH post 30 min of test initiation

#### **8.3.2. PK/PD Analyses**

Analysis for each PK/PD variable will include the following.

- Serum concentrations will be analyzed by evaluating concentration at each time point using continuous descriptive analysis; and by evaluating the PK parameters AUC, Cmax and Tmax using continuous descriptive analysis. This will be done for Visit 1 time points and for basal time points.

- Concentration plots in the original and log scale will be created, combined over subjects (mean and standard deviation) and by subject.
- Additional continuous descriptive analysis will be provided for log transformed values of the PK parameters.
- Burst leuprolide concentrations will be evaluated by examining PK measurements over the first 6 hours post injection.
- Steady state will be evaluated by examining together the leuprolide concentrations collected at each assessment point that are at least one month after the first administration and prior to any Abbreviated GnRHa Stimulation Test or prior to subsequent administration of the leuprolide 45 mg injection solution.
- Change from baseline (screening) for post-baseline basal concentration values will be computed, submitted to continuous descriptive analysis and plotted over each non-baseline time point. Two plots will be created. One will contain means and standard deviations by time point. The second will be a scatterplot displaying individual values at each time point.
- The ratio between prior basal and post GnRHa stimulation concentration will be computed at each available time point, submitted to continuous descriptive analysis and plotted over time points. Two plots will be created. One will contain means and standard deviations by time point. The second will be a scatterplot displaying individual values at each time point.
- The ratio between the basal concentration at screening and post GnRHa stimulation concentration will be computed at each available time point, submitted to continuous descriptive analysis and plotted over time points. Two plots will be created. One will contain means and standard deviations by time point. The second will be a scatterplot displaying individual values at each time point.
- The basal LH to FSH ratio will be computed for each available time point and plotted; and percent change from baseline for this ratio will be computed and plotted. Two plots will be created. One will contain means and standard deviations by time point. The second will be a scatterplot displaying individual values at each time point.
- Further analysis will be accomplished using scatter plots. The pairwise relationship between the various PK/PD variables (leuprolide, LH, FSH, testosterone and estradiol serum concentration) will be captured in scatter plots that use mean concentration values, geometric mean concentration values and individual subject concentration values.

## 9. SAFETY ASSESSMENTS

Selected endpoints described under “Baseline and Related information” also will serve as safety parameters. These endpoints are included in the list below.

- Vital Signs
- Weight
- Physical Examination
- Clinical Laboratory Assessments
- Pregnancy Test
- Adverse Events
- Serious Adverse Events

Categorical descriptive analysis, continuous descriptive analysis and shift table analysis will be applied to safety endpoints as described in Section 7: Planned Study Analyses.

## 10. ANALYSIS POPULATIONS

### 10.1. Safety population

The safety population will consist of all subjects providing consent/assent and who received at least one dose of the study drug.

### 10.2. ITT population

The intent to treat (ITT) population will consist of subjects providing consent/assent who received at least one dose, fulfilled the protocol eligibility criteria, and provided at least one PD laboratory assessment post dosing.

### 10.3. PP population

The per protocol population (PP) will consist of subjects who have received at least one dose of the study medication and have fulfilled the protocol in terms of eligibility, interventions and outcome assessments for at least 6 months.

The table below cross-classifies the various endpoints with the analysis populations.

Table 6 Cross-classification of Various Endpoints with the Analysis Populations

Type of Endpoint	Study Population		
	Safety	Intent to Treat	Per Protocol
Baseline Endpoints		X	X
Primary Efficacy Endpoint		X	X
Secondary Efficacy Endpoint		X	X
Exploratory Efficacy Endpoints		X	X

Safety Endpoints	x		
PK Endpoints		x	

Efficacy will be based on findings using the ITT population. It is noted that for some variables the ITT and PP populations may be identical.

## 11. GENERAL CONSIDERATIONS

### 11.1. Significance Testing

The purpose of this study is to demonstrate suppression of LH at a level of < 4 mIU/mL at 30 minutes after GnRHa stimulation in a majority of subjects ( $\geq 80\%$ ) who are treated with leuprolide acetate 45 mg in an injectable suspension. Inferential statistical testing will not be provided. Rather, descriptive outcomes for the primary and secondary efficacy variables will be used to evaluate the efficacy of this treatment. If requested by the medical writer or the FDA reviewer, inferential significance levels will be formally provided on an *as needed* basis.

### 11.2. Continuous and Presumed Continuous Data

Throughout the study, variables that fall on scales that are or can be presumed to represent continuous dimensions will be captured. Standard descriptive statistics (number of subjects, mean, standard deviation, coefficient of variation, minimum value and maximum value) will be used to characterize continuous and presumed continuous data. In general minimum and maximum will be reported to the numbers of decimal digits as recorded for the original (observed) data; the mean and median will be reported to one decimal digit more than in the original (observed) data; the standard deviation will be reported to two decimal digits; and the coefficient of variation percentage (CV %) will be quoted to one decimal digit.

### 11.3. Categorical Data

Some variables in this study will be captured in the form of a categorical scale. Frequency distributions (number [n] and percentage of subjects [%] for each category) will be used to summarize categorical variables. In general, percentages will be reported to one decimal digit.

### 11.4. Statistical Software

All analyses will be performed using SAS® Software version 9.2 or later.

## 12. IMPUTATION AND MISSING DATA

Unless otherwise indicated, imputation of missing data will not be performed for baseline, efficacy and safety variable values. Each table containing an analysis that reflects an outcome at a given time point in the study will contain only subjects in the analysis population under examination who have data available at that time point.

If a missing concentration datum is surrounded by non-missing values, interpolation will be used in the calculation of AUC, Cmax and Tmax. Otherwise, the nearest non-missing point in time will be used.

If missing date and time values are evident in data not used to develop PK parameters, the following missing date and time algorithm may be applied.

For partial start date/time:

- If the year is unknown, then the date will not be imputed and will be assigned a missing value.
- If the month is unknown, then:
  - If the year matches the year of the dose of study drug date, then the month and day of the dose of study drug date will be imputed.
  - Otherwise, 'January' (01) will be assigned.
- If the day is unknown, then:
  - If the month and year match the month and year of the dose of study drug date, then the day of the dose of study drug date will be imputed.
  - Otherwise, '01' will be assigned.
- If the day is unknown, then:
  - If the month and year match the month and year of the dose of study drug date, then the day of the dose of study drug date will be imputed.
  - Otherwise, '01' will be assigned.
- If the time is unknown, then:
  - If the date (day, month, and year) matches the date of the dose of study drug date, then the time of the dose of study drug time will be imputed.
  - Otherwise, '00' will be assigned.
- For partial stop date/time:
  - If the year is unknown, then the date will not be imputed and will be assigned a missing value.
  - If the month is unknown, then 'December' (12) will be assigned.
  - If the day is unknown, then the last day of the month will be assigned.
  - If the time is unknown, then the last time of the day will be assigned.

If time to an event were needed when only the hour, and not the minutes, are reported for the time of the event, then the minutes will be set to zero.

Any deviations from the implementation of the missing date and time algorithms will be documented in the dataset documentation and final report.

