8.2.3 Criteria for Early Discontinuation

Subjects may be discontinued from the study for any of the following reasons:

1. Parent/guardian(s) and/or subject withdrawal of consent/assent
2. Discretion of Investigator
3. Subject becomes pregnant
4. Changes in the subject's condition that, in the judgment of the Investigator, render the subject unacceptable for further treatment with the study drug
5. Serious adverse event(s) or adverse event(s) that, in the judgment of the Investigator, render the subject unacceptable for further Treatments with the study drug
6. Subject noncompliance with Protocol scheduled visits
7. Termination of the study by the Sponsor, IRB/IEC, or other regulatory authorities
8. Subject fails suppression of LH concentration to <4 mIU/mL (after GnRH α stimulation test) at Visit 3 (~Month 3/Week 12 \pm 7 days)

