8.2.4 Early Discontinuation of Subjects

In the event that a subject is prematurely discontinued from the study, efforts should be made to collect all clinical and laboratory data as scheduled for End of Treatment visit (See [Section 8.4.1](#)) and the subject should be followed up for safety, as appropriate. See [Section 8.5.6.2](#) for details on following up on AEs. In addition, the Investigator should complete and report, as thoroughly as possible, the reasons for withdrawal.

Subjects who discontinue from the study will be treated as per the Investigator's discretion and standard of care for children with CPP.

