8.6.2 Part A, Visit 1 (Baseline, Day 0)—Injection #1

Day 0 Predose:

1. Evaluate hematology, chemistry and urinalysis results from Screening Visit
2. Inclusion/exclusion criteria – review to verify that subject continues to meet all of the inclusion and none of the exclusion criteria.
3. Physical Examination-directed

4. Prior and concomitant medications
5. Vital signs – measured prior to any blood draws
6. Height and weight
7. Urine pregnancy test, females only
NOTE: Results must be negative prior to receiving study drug injection
8. Serum lipids, fasting for ≥ 8 hours (water permitted)
9. Blood samples for basal LH, FSH, testosterone/estradiol concentrations ≥ 30 minutes before planned injection time
10. Predose blood sample for serum leuprolide concentrations ≥ 30 minutes before planned injection time
11. Record all non-treatment emergent AEs from the time of informed consent/assent until first study drug administration

Day 0 Study Drug administration:

12. Pharmacy - prepare study drug for injection (see Pharmacy Manual for complete instructions)
 - a. Remove kit from refrigerator at least 30 minutes prior to planned administration and allow the study drug to reach room temperature
 - b. Start mixing process with the product kit within ≤ 30 minutes prior to the injection time.
13. Apply topical or local anesthetic (per Investigator discretion) to injection site prior to planned injection time; record medication, dose, route, and time
14. Administer first injection of study drug

Day 0 Postdose:

15. Blood sample for LH, FSH, testosterone/estradiol, and serum leuprolide concentrations post study drug injection time:
 - a. 1 hour \pm 5 minutes
 - b. 4 hours \pm 10 minutes
 - c. 6 hours \pm 15 minutes
16. Final AE assessment prior to subject discharge from clinic
17. Schedule/confirm next visit

8.6.3 Telephone Contact 1(14 days \pm 2 days):

1. Query subject or parent: “How have you felt in the last two weeks?” or “How has your child felt in the last two weeks?” Complete [Table 4](#)

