8.6.5 Part A, Visit 3 (~Month 3/Week 12 ± 7 days)

1. Query subject or parent: “How have you felt in the last two weeks?” or “How has your child felt in the last two weeks?” Complete [Table 4](#)
2. Vital signs - measured prior to any blood draws
3. AE and concomitant medications assessments
4. Physical Examination—directed
5. Tanner stage
6. Height and weight
7. Blood samples for basal LH, FSH, testosterone/estradiol concentrations PRIOR to the GnRHa stimulation
8. Blood sample for basal serum leuprolide concentrations PRIOR to the GnRHa stimulation
9. GnRHa stimulation: aqueous leuprolide acetate 20 µg/kg body weight administered SC
10. Blood samples for LH, FSH, testosterone/estradiol concentrations 30 ± 5 minutes AFTER the GnRHa stimulation
11. Schedule/confirm next visit

NOTE: Subjects who do not show adequate suppression of LH concentration to <4 mIU/mL (after GnRHa stimulation test) will be discontinued.

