8.6.10 Part A, Visit 7 (~Month 11/Week 44 ± 7 days)

NOTE: DO NOT complete Part A, Visit 7, if a decision has been made to conduct Part B extension study. In this case, follow procedures for Part B (Visits 7 to 13) beginning in [Section 8.6.12](#).

1. Query subject or parent: “How have you felt in the last two weeks?” or “How has your child felt in the last two weeks?” Complete [Table 4](#)
2. Vital signs - measured prior to any blood draws
3. Height and weight
4. AE and concomitant medications assessments
5. Blood samples for basal LH, FSH, testosterone/estradiol concentrations
6. Blood sample for basal serum leuprolide concentrations
7. Schedule/confirm next visit

8.6.11 Part A, Visit 8 (~Month 12/Week 48 ± 7 days) End of Treatment or Early Discontinuation

1. Query subject or parent “How have you felt in the last two weeks?” or “How has your child felt in the last two weeks?” Complete [Table 4](#)
2. Vital signs – measured prior to any blood draws
3. AE and concomitant medications
4. Physical Examination-complete
5. Tanner stage
6. Height and weight
7. X-ray of non-dominant hand and wrist
8. Urine pregnancy test, females only
9. Clinical laboratory assessments (hematology, chemistry) as per [Appendix 13.1](#)
10. Urine for urinalysis, performed using dipstick supplied by Sponsor
11. Blood samples for basal LH, FSH, testosterone/estradiol concentrations PRIOR to the GnRHa stimulation test
12. Blood sample for serum leuprolide concentrations PRIOR to the GnRHa stimulation test
13. GnRHa stimulation: aqueous leuprolide acetate 20 µg/kg body weight administered SC
14. Blood samples for LH, FSH, testosterone/estradiol concentrations 30 ± 5 minutes AFTER the GnRHa stimulation test

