9.2.5 Accounting for Missing Data

Imputation of missing data will not be performed for baseline, efficacy, and safety endpoints.

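### A child discontinued after non-suppression at Month 3 stays in ITT but has no place in the Month 6 primary percentage, so the rate judged against 80% is conditional on being kept after Month 3

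*SAP*

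**What the plan says.** The Month 3 visit text (Protocol 8.6.5) states: "Subjects who do not show adequate suppression of LH concentration to <4 mIU/mL (after GnRHa stimulation test) will be discontinued". The list in Protocol 8.2.3 includes the same failure, but opens with "Subjects may be discontinued from the study for any of the following reasons".

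The ITT population (SAP 10.2) needs a child to have "received at least one dose, fulfilled the protocol eligibility criteria, and provided at least one PD laboratory assessment post dosing". The post-dose condition is normally met on Day 0, because Protocol 8.6.2 schedules a "Blood sample for LH, FSH, testosterone/estradiol, and serum leuprolide concentrations post study drug injection time" at 1, 4 and 6 hours. SAP 10.3 bases the efficacy conclusion on ITT.

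On missing results, Protocol 9.2.5 says "Imputation of missing data will not be performed for baseline, efficacy, and safety endpoints". SAP 12 says each time-point table "will contain only subjects in the analysis population under examination who have data available at that time point", and SAP 18.2 sets n to subjects with non-missing values.

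For a child who stops early, Protocol 8.2.4 says "efforts should be made to collect all clinical and laboratory data as scheduled for End of Treatment visit". That visit, headed "End of Treatment or Early Discontinuation" (Protocol 8.6.11), includes a stimulation test. SAP 12.3, however, maps early-termination data to scheduled visits for safety variables only.

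Efficacy is claimed if at least 80% of subjects are suppressed at Month 6 (SAP 8.2.1, Protocol 9.2.2). SAP 6.6 and Protocol 9.2 speak of applying the variable to everyone in the study, but give no rule for a child without a Month 6 test.

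**The concern.** This is not ordinary missing data. The protocol can remove children on the endpoint variable, at the endpoint's own cut-off, three months before the endpoint is measured. The available-data rule then drops them from the percentage. There is no control arm and no inferential test (SAP 6.5, 11.1), so that one percentage carries the whole Part A efficacy decision.

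The per-protocol analysis does not help. It requires outcome assessments for at least six months (SAP 10.3), so it omits the same children.

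At stake is whether efficacy could be claimed when fewer than 80% of ITT children were suppressed. The scope is the Month 6 percentage, which is primary if the study ends with Part A and secondary if Part B is invoked.

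**Working it through.** **Inputs from the documents.** The bar is 80%. About 40 children are to be evaluable at six months, from about 60 screened and/or enrolled (Protocol synopsis). The expected response is 85% to 90% (SAP 6.7). About 70% suppression is called clinically important (Protocol 9.1, SAP 6.7).

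**Assumptions, because the documents give no figure.** q is the share of ITT children removed after Month 3 failure. r is the share of those removed who would have been suppressed at Month 6. The number dosed, N, runs from 40 to 60. Nothing else is missing.

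**The plan's own figure.** SAP Table 4 uses L = P − [1.645·√(P(1−P)/n) + 1/(2n)]. For n=25, P=0.85: 0.85 − (0.1175 + 0.0200) = 0.7125 (stated 0.713). For n=40, P=0.85: 0.7446 (stated 0.745). All twelve rows agree within 0.001. The table is arithmetically sound, but its n is the final sample after dropout, so it says nothing about children who were removed.

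**What a reported 80% means for ITT.** ITT rate = 0.80(1−q) + r·q.

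| q | r=0 | r=0.5 |
|---|---|---|
| 0 | 80% | 80% |
| 5% | 76% | 78.5% |
| 10% | 72% | 77.0% |
| 15% | 68% | 75.5% |

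Setting the rate to 0.70 gives q = 0.10/0.80 = 12.5% at r=0, and q = 0.10/0.30 = 33% at r=0.5.

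**How many failures reverse the claim.** With x of 40 tested children suppressed and k Month 3 failures, find the smallest k for which (x + r·k)/(40 + k) < 0.80. Counting failures as not suppressed is r=0.

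| x of 40 | k at r=0 | k at r=0.5 |
|---|---|---|
| 32 | 1 (32/41 = 78.0%) | 1 |
| 33 | 2 (33/42 = 78.6%) | 4 |
| 34 | 3 (34/43 = 79.1%) | 7 |
| 35 | 4 (35/44 = 79.5%) | 11 |
| 36 | 6 (36/46 = 78.3%) | 14 |

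**Chance of a claim.** Let T be the all-ITT rate at Month 6. Retained children M ~ Bin(N, 1−q); suppressed X given M ~ Bin(M, p), with p = (T − q·r)/(1−q). As planned, the chance is P(X/M ≥ 0.80). The comparison is P(Bin(N,T)/N ≥ 0.80), which at r=0 is the failures-counted rule.

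| T, q (r=0) | N=40 | N=45 | N=60 |
|---|---|---|---|
| 90%, 5% | .999 v .985 | >.999 v .988 | >.999 v .994 |
| 85%, 2% | .894 v .865 | .904 v .873 | .930 v .894 |
| 85%, 5% | .962 v .865 | .970 v .873 | .985 v .894 |
| 80%, 5% | .770 v .593 | .783 v .588 | .817 v .576 |
| 75%, 10% | .730 v .300 | .739 v .280 | .762 v .232 |

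Over every N from 40 to 60, with T of 85% or 90%, q of 2% or 5% and r=0, the gap runs from .004 (T=90%, q=2%, N=60) to .176 (T=85%, q=5%, N=44). N=44 is extreme because its bar is 36/44 = 81.8%. At r=0.5 the same settings give −.011 (T=85%, q=2%, N=40: .854 v .865) to .110 (T=85%, q=5%, N=44). The negative values come from discreteness.

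These ranges treat 85% to 90% as the all-ITT rate. If 85% is instead the rate among retained children, then at q=5%, r=0 and N=40 the ITT rate is 0.95 × 0.85 = 80.75% and the chances are .810 v .640.

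**The case against.** **The denominator may already be everyone.** SAP 6.6 and Protocol 9.2 can be read that way. They do not say how to score a child with no Month 6 result, while SAP 12 does state who enters a table, and no exception for the primary endpoint follows. At best the texts conflict.

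**Discontinuation may not be automatic.** Protocol 8.2.3 is permissive. A child who is kept has a Month 6 result and is counted, so the problem reaches only children actually removed. Under that reading, two children with the same Month 3 result could be scored differently. This stands, and it is a reason to reconcile the two passages.

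**The failures will be visible.** The Month 3 percentage (SAP 8.2.2), terminations by reason (SAP 14.3) and the baseline comparison of unavailable children (SAP 16) will show them. This is true, but none of these changes the percentage on which the claim rests.

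**The 80% bar has a margin.** Protocol 9.1 calls it conservative because dropout is unknown, and treats about 70% as clinically important. This bears on seriousness: a reported 80% falls to 70% of ITT only at q=12.5% (r=0) or 33% (r=0.5). It does not define the denominator.

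**The size is unknown.** This is correct. A reader might infer that the plan will inflate the result, or that gaps such as .730 v .300 are typical. The documents support neither reading. They give no q or r, r=0 is the least favourable case, and a 75% rate lies below the plan's expectation.

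**The trigger and endpoint are tied together.** Both documents describe one variable for the Part B decision and for efficacy. Changing only the final percentage would contradict those sentences unless they are amended too. This stands and is met in the fix.

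**Conclusion.** The point holds as a gap in the definition of the Month 6 percentage. As written, an eligible child removed after Month 3 failure is in ITT but uncounted, and the figure judged against 80% is the rate among children kept after Month 3. It overstates the ITT rate if removed children would be suppressed less often than retained ones. That is plausible given why they were removed, but their Month 6 status is not observed.

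The size rests on q and r. It is nil at q=0, or if removed children would do as well as retained ones. Near the bar, one to three failures counted as not suppressed would reverse a claim at 32 to 34 of 40. In the expected 85% to 90% range, taken as the all-ITT rate with q of 2% to 5%, r=0 and 40 to 60 dosed, the chance of a claim is higher as planned by about .004 to .18. At r=0.5 it is generally smaller and can be slightly negative.

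The rule should be settled in advance, because afterwards the choice of denominator could decide the claim.

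**What to change.** Reconcile Protocol 8.2.3 with 8.6.5; this review takes no position on which should stand.

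In SAP 6.6, 8.2.1 and 12, and Protocol 9.2, 9.2.2 and 9.2.5, state the following:

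- An ITT child whose stimulated LH is not below 4 mIU/mL at Month 3, and who is discontinued before the Month 6 test, counts as not suppressed in the Month 6 percentage, whatever reason for stopping is recorded.
- This applies whether that percentage is primary or, with Part B invoked, secondary.
- An observed scheduled Month 6 result is never overridden.
- The available-data percentage is reported as supportive.
- A sensitivity analysis counts all other missing Month 6 tests as not suppressed.

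Amend the sentences in SAP 6.6 and Protocol 9.2 that use one variable for both purposes. They should say expressly that the interim Part B trigger stays on subjects with data through Month 6, while the final Month 6 percentage uses this composite definition.

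The cost is a SAP revision and a protocol amendment, which needs IRB/IEC approval before implementation (Protocol 10.6). No new data are needed. If Month 3 failures occur, the reported percentage may be less favourable and could fall below 80%.

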7.2 Secondary Objectives

[figure not shown]
- Evaluate the safety and tolerability of leuprolide acetate 45 mg for injectable suspension in children with CPP
- Characterize the burst kinetics of leuprolide acetate 45 mg after the first administration
- Characterize the pharmacodynamic (PD) relationship of leuprolide serum concentrations to concentrations of serum LH, FSH and to testosterone/estradiol
- Assess percent changes in height velocity and bone age progression after the first administration
- Assess changes in physical signs of puberty as measured by changes in Tanner stages or in changes or onset of menses
- Determine the dosing interval (5 or 6 months) at which leuprolide acetate is able to suppress LH concentration to <4 mIU/mL (after GnRHa stimulation test), as data permit

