8.2.1 Subject Inclusion Criteria

Subjects must meet all of the following criteria to be eligible for participation in the study:

1. Females age 2 to 8 years (inclusive) or males age 2 to 9 years (inclusive)
2. Confirmed diagnosis of CPP within 12 months of Baseline Visit (Day 0) but have not received prior GnRH agonist treatment for CPP
3. Pubertal-type LH response following an abbreviated GnRHa stimulation test before treatment initiation > 5 mIU/mL
4. Clinical evidence of puberty, defined as Tanner stage ≥ 2 for breast development in females or testicular volume ≥ 4 mL in males
5. Willing and able to participate in the study
6. Difference between bone age (Greulich and Pyle method) and chronological age ≥ 1 year
7. Signed IRB/IEC-approved ICF by one or both parents (per IRB/IEC requirements), by the custodial parent or by the legal guardian(s) (if required)
8. Signed Assent by subjects as per IRB/IEC requirements

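### The SAP's nearest-value rule turns a missed pre-dose leuprolide sample into the 1 h burst value, and nothing flags burst parameters derived without the 1 h sample

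*SAP*

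**What the plan says.** SAP section 12 rules out imputation for baseline, efficacy and safety variables unless otherwise indicated, then gives a separate rule for concentrations. For an interior gap: "If a missing concentration datum is surrounded by non-missing values, interpolation will be used in the calculation of AUC", and likewise for Cmax and Tmax. For any other gap: "Otherwise, the nearest non-missing point in time will be used". The rule has no exception for a sample taken before an injection. It does not say whether interpolation is linear or logarithmic, and it asks for no flag on a parameter derived with a filled value. The no-imputation statement in Protocol 9.2.5 covers baseline, efficacy and safety endpoints, so it does not switch this rule off for PK.

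The Visit 1 series is pre-dose, 1, 4 and 6 h (Protocol Table 2; SAP 8.3.1). Protocol 8.6.2 places the first of these as follows: "Predose blood sample for serum leuprolide concentrations ≥ 30 minutes before planned injection time". The SAP 8.3.1 parameters for this series include AUC and Tmax over six hours and "Cmax over six hours". SAP 8.3.2 adds: "Burst leuprolide concentrations will be evaluated by examining PK measurements over the first 6 hours post injection". The objective served is a secondary one in Protocol 7.2: "Characterize the burst kinetics of leuprolide acetate 45 mg after the first administration".

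**The concern.** The pre-dose sample is at the edge of the Visit 1 series, so the nearest-value rule governs it, and its nearest neighbour was taken after the injection. Under Protocol 8.2.1 these children "have not received prior GnRH agonist treatment for CPP". Taken literally, the rule gives such a child a burst-level concentration before any study drug has been injected. The rule itself creates that error.

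A second, separate weakness concerns the peak. An interpolated value never exceeds the larger of its two neighbours, so filling a gap cannot restore a missed maximum. Cmax and Tmax would still be reported alongside those from complete profiles.

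Each child has one four-point profile, so a single filled point weighs heavily in that child's burst parameters.

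**Working it through.** The documents give no concentrations and no figure for this point, so there is nothing to reproduce. The check applies the section 12 rule to assumed profiles and reports ranges.

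**Inputs**
- Sampling times 0 (pre-dose), 1, 4 and 6 h: Protocol Table 2, SAP 8.3.1.
- True pre-dose leuprolide of 0: assumed, for children without prior GnRH agonist treatment.
- Five profile shapes in relative units: assumed.
- Linear interpolation and linear trapezoid: assumed, as the SAP names neither.

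**Formula.** AUC0-6 = 0.5(C0 + C1)×1 + 0.5(C1 + C4)×3 + 0.5(C4 + C6)×2.

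**Step 1: pre-dose missing.** C0 becomes C1. The first term goes from 0.5×C1 to C1, so AUC0-6 rises by 0.5×C1.

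**Step 2: 1 h missing.** With C0 = 0, C1 becomes C4/4. True AUC minus filled AUC is 0.5×C1 + 1.5(C1 + C4) − 2×C4 = 2×C1 − 0.5×C4. AUC therefore falls only if C1 exceeds C4/4.

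| Assumed profile (0/1/4/6 h) | True AUC0-6 | Pre-dose missing | 1 h missing |
|---|---|---|---|
| 0/100/60/40 | 50+240+100 = 390 | 440 (+12.8%) | 220 (−43.6%) |
| 0/100/100/100 | 50+300+200 = 550 | 600 (+9.1%) | 400 (−27.3%) |
| 0/50/100/80 | 25+225+180 = 430 | 455 (+5.8%) | 380 (−11.6%) |
| 0/20/100/90 | 10+180+190 = 380 | 390 (+2.6%) | 390 (+2.6%) |
| 0/30/80/100 | 15+165+180 = 360 | 375 (+4.2%) | 340 (−5.6%) |

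If the area is integrated from −0.5 h, the time of the latest permitted pre-dose draw, a missing pre-dose value adds 0.75×C1, which is +3.9% to +18.1% over the same profiles. The threshold in step 2 becomes C4/3.

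**Step 3: Cmax and Tmax.** With pre-dose missing, the filled value equals C1, so Cmax cannot change. In the first two profiles 1 h is the maximum, so the filled value ties with it, and taking the first maximum puts Tmax at the pre-dose time. With 1 h missing in the first profile, Cmax falls from 100 to 60 and Tmax moves from 1 h to 4 h. Where the peak is at 4 h or 6 h, neither changes.

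**Step 4: is the 1 h loss due to the rule?** Leaving the sample out of the first profile gives 0.5(0 + 60)×4 + 100 = 220, the same as interpolating. Cmax and Tmax also match.

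**Step 5: does the screening sample rescue the pre-dose value?** If it counted as a surrounding value, with leuprolide 0 at T hours before injection, the interpolated pre-dose value would be C1×(T − 0.5)/(T + 1). For T = 24 h that is 23.5/25 = 94.0% of C1. For T = 672 h (28 days) it is 671.5/673 = 99.8%. The result is almost the same.

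**The case against.** The pre-dose draw is a scheduled clinic step immediately before the injection, so it may seldom be missed; the documents give no rate. The analysis is descriptive, and SAP section 7 already expects more variable PK parameters because sampling is limited. Both points reduce the importance of the issue. Neither answers it: a pre-dose value replaced by a burst value is an error in one direction, not extra variability.

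The strongest objection concerns the 1 h sample. A reader might infer that the rule makes every profile with a missing 1 h sample understate the burst. The documents do not support that. The direction depends on the shape of the profile, which is unknown, and step 4 shows that linear interpolation loses exactly what omission loses. The loss comes from the absent sample. What stands is that the SAP does not mark such a profile as incomplete.

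A reader might also infer that a missing Week 4 sample would be filled on a line from the 6 h burst sample to the Week 12 trough. With assumed values of 60 at day 0.25 and 0.5 at day 84, that gives 60 − 59.5×27.75/83.75 = 40.3. However, SAP 8.3.1 builds the basal series from screening, the first Visit 1 measurement and Visit 2 onward, and the 6 h sample is not in it. From a pre-dose 0, the filled value is 0.5×28/84 = 0.17. The AUC sub-items under that heading leave some ambiguity. Even so, adding a point on a straight line leaves a linear-trapezoid AUC unchanged, and 40.3 below an observed 60 cannot alter Cmax or Tmax. Section 12 also restricts by-time-point tables to subjects with data at that time, so the value would not be tabulated as a trough.

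**Conclusion.** The concern holds for the pre-dose sample. As written, the rule overstates that child's AUC0-6 by half the 1 h concentration, about 3% to 13% when integrated from 0 h, and can place Tmax before the injection. The effect on a group mean is diluted by the share of children affected, which cannot be known from the documents.

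For a missing 1 h sample the point is conditional. If 1 h is the peak, all three parameters are wrong in the directions shown, and they go unflagged.

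The percentages rest on assumed profile shapes, a true pre-dose value of zero and linear methods. The addition of half of C1 needs only the last two of these.

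The consequence is confined to descriptive summaries for the burst-kinetics objective. It would be wrong to read this as touching the primary result: the LH responder percentage is an efficacy variable, and section 12 does not impute those.

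**What to change.** Amend SAP section 12 in two places.

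1. Exempt pre-dose samples from the nearest-value rule, and set a missing pre-Injection #1 leuprolide concentration to zero. State the assumption that the screening stimulation dose has cleared: each child receives 20 µg/kg leuprolide at screening, and no minimum gap before Day 0 is given. Limit the zero to leuprolide. SAP 8.3 applies the same parameters to LH, FSH and sex steroids, whose pre-dose values cannot be taken as zero.
2. Take Cmax and Tmax from observed samples only, and flag AUC0-6, Cmax and Tmax when the 1 h sample is missing.

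The existing rules for AUC should stay where the 4 h or 6 h sample is missing. With an assumed profile of 0/100/80/60, the true AUC0-6 is 50+270+140 = 460.
- **6 h missing:** the SAP rule gives 50+270+160 = 480 (+4%). A trapezoid over observed samples alone stops at 4 h and gives 50+270 = 320 (−30%).
- **4 h missing:** interpolation gives 50+400 = 450 (−2%), with Cmax and Tmax correct. Declaring such a profile not estimable is not justified.

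The cost is a small change of SAP wording and a few flagged profiles. No sampling or visit procedure changes.
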